### 7.3 **Bleeding**

7.3.1 Major bleeding will be defined as:

- a) Bleeding into critical organs such as central nervous system, retroperitoneum
- b) Bleeding requiring emergent intervention or surgery for hemostasis
- c) Bleeding requiring at least 2 units of packed red blood cell transfusion
- d) Bleeding leading to at least 2 points drop in hemoglobin from baseline
- e) Bleeding requiring hospital admission for intervention

7.3.2 Non-major bleeding is defined as any other bleeding reported by patients but not otherwise meeting the above listed criteria for major bleeding

## **8.0 Treatment after Recurrences of VTE**

Patients suffering a recurrent VTE on either arm will stop study drugs and but will continue to be followed on the study. The management of recurrent VTE will be left to the discretion of the treating physician.

## **9.0 Correlative Studies**

### **9.1 Laboratory Studies at Enrollment**

9.1.1 The initial laboratory tests will be obtained at the time of enrollment on this study. Blood will be collected after overnight fasting for at least 9 hours. Laboratory tests will include:

- CBC (complete blood count)
- chemistry panel (Na, K, Cl, CO2, Cr, BUN, Ca, and glucose),
- liver function tests (AST, ALT, ALP, total and direct bilirubin)
- D-dimer
- high-sensitivity C-reactive protein (hs-CRP)
- fasting lipid profiles (LDL, HLD, TG, total cholesterol)
- β-hCG is required only in women of child-bearing potential

*Research labs:*

- thrombin generation assay
- IL-6, IL-8, tumor necrosis factor (TNF)-α
- lipidomic profiles including free fatty acids, lipoprotein-associated phospholipase A2, pro-inflammatory eicosanoids
- plasma levels and RNA expression of tissue factor (TF), tissue factor pathway inhibitor (TFPI), and other clotting factors

### **9.2 Subsequent Follow-up and Correlative Laboratory Studies**

9.2.1 All enrolled patients will be seen on enrollment and at month 3 and 9.

9.2.2 The following laboratory studies will be obtained at each follow-up visit:

- CBC (complete blood count), platelet count
- chemistry panel (Na, K, Cl, CO2, Cr, BUN, Ca, and glucose),
- liver function tests (AST, ALT, ALP, total and direct bilirubin)
- d-dimer
- high-sensitivity C-reactive protein (hs-CRP)
- fasting lipid profiles (LDL, HLD, TG, total cholesterol)

*Research labs:*

- thrombin generation assay
- IL-6, IL-8, tumor necrosis factor (TNF)- $\alpha$
- lipidomic profiles including free fatty acids, lipoprotein-associated phospholipase A2, pro-inflammatory eicosanoids
- plasma levels and RNA expression of tissue factor (TF), tissue factor pathway inhibitor (TFPI), and other clotting factors

9.2.3 A follow up Doppler ultrasound will be obtained at month 3 as standard of care in all patients to evaluate residual vein thrombosis.

## **10.0 Outpatient Visits**

Patients will be seen in the outpatient thrombosis clinic at least on enrollment, month 3, and month 9 (conclusion of the study), at each time side effects of drugs, symptoms of bleeding and recurrent VTE, post thrombotic syndrome will be assessed. Pill count and drug compliance will be assessed as well. Enrollees will be given \$6 dollar food vouchers to be used in the cafeteria for each of the scheduled study visit (enrollment, 3 and 9 months) to compensate their efforts of fasting prior to lab drawn.

## **11.0 Safety Monitoring During Study**

11.1 To ensure the safety of all patients enrolled on this study, careful monitoring and follow-ups for all patients will be important aspects of this study. Patients will be monitored closely with laboratory and clinical evaluations at regular intervals defined in the study protocol.

11.2 At each visit (enrollment, 3 and 9 months), patients will be evaluated by physicians and study personnel for side effects of statins and anticoagulation. The management of side effects from statins will follow the routine practice for patients who are prescribed with statins for other medical problems, and will be left to the discretion of the treating physicians, but the study team and PI will be available for any assistance if questions of the optimal management of adverse events were to arise. Liver function tests will be obtained prior to and at each follow-up visit. Creatine kinase (CK) test will not be collected without symptoms, but will be collected if patients were to develop symptoms of muscle pain or weakness. Patients with new onset of transaminitis or CK above three times of upper limit of normal or significant symptoms will be taken off statins. Their abnormal laboratory tests will be monitored at least every 2 weeks, more frequently if needed, until the abnormalities resolve. Patients will only resume statins if their symptoms resolve, blood tests normalize, and if patients are willing to resume treatment. Recurrent test abnormality or symptoms will require permanent discontinuation of statins.

## **12.0 Adverse Events/Severe Adverse Events**

12.1 *Definition:* Adverse events as defined in the International Council on Harmonisation Guidelines for Good Clinical Practice are described as “an untoward medical occurrence in a patient or clinical investigation administered a pharmaceutical product that does not necessarily have a causal relationship with this treatment.”

12.2 A serious adverse event is an adverse event that:

- Is fatal
- Is life threatening (places the subject at immediate risk of death)
- Results in inpatient hospitalization or prolonged existing hospitalization
- Results in persistent or significant disability/incapacity
- Is a congenital anomaly/birth defect
- Includes other significant hazard

12.3 *Grading of Adverse Events* – Events will be graded by using the Common Terminology Criteria for Adverse Events (CTCAE) Criteria version 4.0.

12.4 *Attribution* – the determination and documentation of whether an adverse event is related to a medical procedure.

### Attribution Categories:

1. Not Related –Event clearly related to other factors (e.g., clinical state, other therapies; concomitant drugs)
2. Possible Related – Sequence of event is compatible with study drug, device, or procedure, but could have been produced by other factors
3. Probably Related - Sequence of event is compatible with study drug, or procedure and cannot be explained by other factors without much doubt
4. Definitely Related - Sequence of event is compatible with study drug, or procedure and beyond doubt cannot be explained by other factors

12.5 *Reporting of Adverse Events:* Adverse events must be recorded within 7 days of the occurrence using the “Adverse Event” form (see Appendix). The principal investigator will review all adverse event forms every month or more frequently if needed. All serious or unexpected adverse events must be communicated to the principal investigator immediately and will be reported to the IRB within 24 hours of learning of the event’s occurrence by phone, email, or SAE for regardless of attribution. Using these mechanisms of rapid reporting, we will be able to rapidly evaluate and minimize the potential risks to patients from the occurrence of these events. Subjects will be instructed to report any adverse event(s) during the study and post-study. The investigator will notify the IRB of any unanticipated death or adverse event occurring after a participant has discontinued or terminated study participation that may reasonably be related to the study.

12.6 *Follow-up of Adverse Events:* Patients experiencing an adverse event will continue to be followed and carefully monitored until the resolution of the adverse event. This applies whether the patient continues on study or is removed from the study for any reason.

12.7 While no formal stopping rules are deemed necessary due to the well-known safety and tolerability of statins, the PI will be informed of any SAE immediately, determine correlation, and report to IRB. The PI is responsible to continuously evaluate the safety for study continuation based on regular review of AE reports.

### **13.0 Sample Procurement**

Both plasma and blood samples will be taken as a part of this protocol. These samples will be obtained at the same time that standard clinical samples or procedures are being performed so patients will not be exposed to additional venipunctures or procedures by their participation in this study.

### **14.0 Sample Storage and Handling**

At the time of enrollment and registration with the coordinating institution, arrangements will be made for the research blood samples to be delivered to the laboratory of [name], [name], and [name] for processing and analysis. Research blood samples will be labeled with a unique identification number so that the data obtained may be correlated with the patient's clinical course by the investigators at the end of the study, while the laboratory personnel performing the research testing will not be able to identify each individual patient. This will help ensure patient confidentiality, as the investigators will be the only people to know the patient name and medical record number that correspond with the identification number. Samples to be used for future study will be frozen at -80°C and be stored in the benign hematology research office at the James Cancer Hospital, and in the laboratory of [name], depending on the designated research testing to be done: thrombin generation assays will be performed in [name] laboratory at Nationwide Children's. Inflammatory markers will be done in [name] laboratory at Nationwide Children's and lipidomic profiles will be performed at [name] laboratory at Ohio State. At the end of the study, at least one aliquot of each plasma and RNA samples will be delivered to [name] laboratory at the Blood Center of Wisconsin for testing including TF, TFPI, and other clotting factors. Samples will be sent on dry ice via commercial carriers overnight.

### **15.0 Risks Associated with Testing of Patient Samples**

A breach of confidentiality is the most serious risk which patients may be exposed to regarding to research testing of biologic samples. Confidentiality will be maintained by labeling the patient samples with only an identification number and not their name or medical record number. By using this approach, patient samples may be tied to clinical information by the investigators but will preserve the confidentiality of patients. Only the principal investigator, co-investigator, and the study nurse/coordinator will have access to both the study number and the corresponding patient identification information. Clinical

information or laboratory data used for publication will not identify patients in any way that could potentially breach patient confidentiality. The samples sent to BloodCenter of Wisconsin will be coded and all PHI will be removed so the laboratory personnel there will have no access to the PHI. The samples need to be coded and not de-identified, so the principal and co-investigators can correlate clinical with research laboratory findings. Even though more research laboratory tests are planned in this protocol amendment, it will be accomplished within the same amount of blood that was originally planned to be drawn and therefore expose no additional risks to subsequent enrollees.

## **16.0 Thrombin generation assay**

Blood samples for measurement of thrombin generation will be drawn in vacutainer tubes containing 3.2% sodium citrate with and without corn trypsin inhibitor (CTI) and be processed appropriately within an hour prior to storage. Blood samples will be centrifuged at 2500g (relative centrifugal force) for 15 minutes (min). Plasma will be transferred into plastic tubes, and re-centrifuged at 2500g for 15 min. Plasma will be decanted again after second spin and stored in aliquots of 0.2 mL (platelet poor plasma). The platelet poor plasma will then be snap frozen and stored at -70°C until testing as bulk at the end of the study.

The thrombin generation assays will be performed using a commercial kit (TECHNOTHROMBIN® TGA, Technoclone, Vienna, Austria) according to the manufacturer's instructions in [name] laboratory. The assays are performed based on monitoring the fluorescence generated by thrombin cleavage of a fluorogenic substrate over time, after the activation of the coagulation cascade by tissue factor. At least two reagents will be used. Parameters that will be recorded include: lag phase, time to peak thrombin concentration, peak thrombin concentration, and endogenous thrombin potential (measured by area under the curve).

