## Schema

## 1.0 Objectives

*This will be a single-center, open-labelled, pilot study. This study has the following objectives:*

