### 1.1 Primary Objective

1.1.1 To determine the reduction of thrombin peak concentration and/or endogenous thrombin potential measured by Thrombin Generation Assay (TGA) at 3 months in the “anticoagulation +atorvastatin” arm as compared to the “anticoagulation” arm.

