**20.0 Statistical Analysis**

At least 66 evaluable patients will be randomized (1:1 allocation, 33 evaluable patients in each arm) into "anticoagulation" versus "anticoagulation +atorvastatin" arms. The primary endpoints are thrombin peak and thrombin generation. Based on the published data, we anticipate an 80% power to detect an effect size of 0.7 standard deviations in the reduction of thrombin peak or thrombin generation between the two arms with two-side alpha of 0.05 using a two-sample t test. An overall alpha of 0.1 for this pilot study was split into 0.05 for each endpoint (thrombin peak and thrombin generation) using Bonferroni method. Considering possible drop-outs, our target enrollment will be 80 patients, with 40 on each arm.

All data will be collected on study-approved data collection forms and entered into Research Electronic Data Capture (REDCap), which is a secure, web-based application designed to support data capture for research studies by building and managing online surveys and databases. The system was built with the help of the OSU Research Informatics Services.

Descriptive statistics (i.e. means, standard deviations, 95% confidence intervals for continuous variables, and frequencies for discrete data) and graphical analyses will be used for all clinical outcomes, demographics, VTE related events, laboratory results, and adverse events for each arm. The secondary endpoints will be compared between the two arms using chi-square test or Fisher's exact test, whichever is appropriate. The associations between treatment type and the change in biomarkers will be evaluated using two-sample t test. Log-transform will be used if necessary. Linear mixed models will be used to study the associations between the primary endpoints and treatment, and trend across time. The interaction term "arm x time" will be included in the model to study whether the two treatment arms have different "behavior" across time. Potential confounders will be included in the models. Thrombin peak concentration and

endogenous thrombin potential at 9 months will be compared between the patients on anticoagulation and those off anticoagulation.

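### Do the unspecified assay reagents and tube types undermine the 0.10 overall alpha for the two primary thrombin endpoints?

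*Combined protocol and SAP*

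**What the plan says.** The primary objective (Section 1.1) is "To determine the reduction of thrombin peak concentration and/or endogenous thrombin potential measured by Thrombin Generation Assay (TGA) at 3 months", compared between the two arms. Section 20.0 sizes the trial at 33 evaluable patients per arm for 80% power at 0.7 standard deviations, "with two-side alpha of 0.05 using a two-sample t test". It then sets the multiplicity rule: "An overall alpha of 0.1 for this pilot study was split into 0.05 for each endpoint (thrombin peak and thrombin generation) using Bonferroni method".

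Section 16.0 describes the assay. Blood is "drawn in vacutainer tubes containing 3.2% sodium citrate with and without corn trypsin inhibitor (CTI"), and the plasma is "snap frozen and stored at -70°C until testing as bulk at the end of the study". One commercial kit is used, and then comes the sentence "At least two reagents will be used". Peak and endogenous thrombin potential (ETP) are among four recorded parameters. None of the four is tied to a reagent or a tube type.

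Section 20.0 calls the second endpoint thrombin generation. Read with Section 1.1, and with the closing sentence of Section 20.0 ("endogenous thrombin potential at 9 months will be compared between the patients on anticoagulation and those off anticoagulation"), it means ETP.

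**The concern.** A Bonferroni split controls error over a fixed list of tests. Section 20.0 lists two. Section 16.0 appears to lengthen the list: two tube types, or two reagents, would give two versions of each endpoint and four possible tests. Both factors crossed would give eight. No section names the version that counts or says how several values per patient would be combined.

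The trial is described as a "single-center, open-labelled, pilot study", the primary objective is worded so that either endpoint may succeed, and the assays are run together at the end. If the version were picked after results were seen, a reader could not tell a planned positive result from a selected one, and the stated 0.10 would not be assured.

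**Working it through.** **1. Reproduce the plan's figures.** Inputs from Section 20.0: effect 0.7 SD, two-sided 0.05, power 80%, 33 per arm.

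- Normal approximation: n = 2 × (1.960 + 0.842)² / 0.7² = 32.04, rounded up to 33 per arm.
- Exact noncentral t, 64 degrees of freedom, noncentrality 0.7 × √(33/2) = 2.84: power 79.97%.
- Alpha: 0.05 + 0.05 = 0.10. If the two tests were independent, the family-wise error would be 1 − 0.95² = 9.75%. At correlation 0.7 it is 8.35%.

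The plan's sample size and alpha split are correct as written.

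**2. Error if any version could count.** This decision rule is hypothetical. Take k test statistics, jointly normal with common correlation ρ, each tested at two-sided 0.05. For ρ = 0 the error is 1 − 0.95^k. For ρ > 0 it is one minus the integral over u of φ(u) × [Φ((1.96 − √ρ·u)/√(1−ρ)) − Φ((−1.96 − √ρ·u)/√(1−ρ))]^k. The documents give no correlations, so ρ is an assumed range.

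| ρ | k = 2 | k = 4 | k = 8 |
|---|---|---|---|
| 0 | 9.75% | 18.5% | 33.7% |
| 0.7 | 8.35% | 13.0% | 19.1% |
| 0.8 | 7.8% | 11.4% | 15.7% |
| 0.9 | 7.0% | 9.4% | 11.9% |
| 0.95 | 6.5% | 8.0% | 9.5% |

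The error crosses 10% at ρ = 0.872 for four tests and at ρ = 0.941 for eight.

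**3. A more realistic structure for four tests.** Versions of one endpoint should correlate more strongly than peak does with ETP. Taking the correlation matrix as the product of the two, simulation gives:

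| Between versions | Peak–ETP 0.7 | Peak–ETP 0.8 | Peak–ETP 0.9 |
|---|---|---|---|
| 0.9 | 11.6% | 10.8% | 9.8% |
| 0.95 | 10.7% | 10.0% | 9.0% |

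Under these assumptions the excess over 10% is at most about 1.6 percentage points, and in some cells there is none.

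**4. What would change if the condition were named.** One reagent and one tube type per endpoint, or one averaging rule fixed beforehand, leaves two tests at 0.05. Alpha, 33 per arm and 80% power are the same as now. The alternative of treating four versions as co-primary at 0.10/4 = 0.025 each would cut power at 33 per arm to 70.7% and need 41 per arm for 80%. Nothing in the plan asks for that.

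**The case for a change.** The best case for a change is that the sponsor chose formal error control, so the plan ought to fix the two measurements to which it applies. The number of reagents has no upper limit. Reading the reagent sentence as a mere reference to kit components would make it redundant, because the kit is already to be run by the manufacturer's instructions. Even on that reading, two tube types remain. Section 14.0 keeps laboratory staff from identifying patients, but that does not stop a choice of version at the analysis stage, where investigators can link results to patients.

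Much of this stands. The primary assay condition is not stated anywhere, and 0.10 is not guaranteed under every conceivable use of the data. Three things limit its force.

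- Section 20.0 names two endpoints, one alpha for each and one test. It does not allow any version to count, so the error rates in step 2 describe a misuse and not the planned analysis.
- Reagents are not defined, and no section says that every reagent is run on both plasmas. The eight-test case needs both assumptions. Section 16.0 says that both tube types are drawn, not that both supply primary values.
- The independence figures of 18.5% and 33.7% are the least plausible ones, since peak and area come from the same curve in the same patients.

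It would also be wrong to say that the level holds only when a single condition is fixed. At high enough correlation even unrestricted testing stays below 10%, and a pre-stated average would also leave two tests.

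**Conclusion.** No change to the plan is needed. This is an unstated assay detail in a pilot study with a deliberately relaxed overall alpha. The two-test split, the 0.05 per endpoint, the 33 per arm and the 80% power are right as they stand, and no stated rule produces a wrong result. The analysts and the laboratory have to choose a primary condition in order to build the data set. Because the samples are assayed in bulk at the end, they can do so before any thrombin generation result exists. The use of thrombin generation for ETP in Section 20.0 is loose wording that Section 1.1 resolves.

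The conclusion rests on taking Section 20.0 at its word, as one test for each of two endpoints. If any of four versions could count instead, the error would be about 9% to 12% with correlations of 0.9 or 0.95 between versions and 0.7 to 0.9 between peak and ETP. It would be higher with lower correlations or with eight tests. All these correlations are assumptions. When the results are reported, it is reasonable to check that one condition is identified as primary and the others are shown as supportive.

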## **17.0 Inflammatory marker assessment**

Serum IL-6, IL-8, and TNF- $\alpha$  levels will be measured using commercial enzyme-linked immunosorbent assay (ELISA) according to the manufacturer's instructions in [name] laboratory.

## **18.0 Lipidomic profiles**

18.1 Lipidomic profiles will be done in [name] laboratory. Blood samples for measurement of lipidomic profiles will be drawn in two vacutainer tubes, one containing 3.2% sodium citrate and the other being a serum separator tube.

After collection, blood will be separated into individual constituents including serum. Lipidomic profiles will be collected on blood samples using a triple quadrupole mass spectrometry platform called Lipidzyzer which is enabled through ion mobility hardware. This assay covers 13 different lipid classes and uses 56 stable isotope internal standards to provide quantitative results for as many as 1,100 lipid species. A separate LCMS panel will be utilized to determine eicosanoid profiles in blood. Both of these

assays will be conducted in the Nutrient & Phytochemical Analytic Shared Resource (NPASR) of the OSU Comprehensive Cancer Center under the direction of Acting Director, [name]..

**19.0 Plasma levels and RNA expression of tissue factor (TF), tissue factor pathway inhibitor (TFPI), and other clotting factors**

19.1 These tests will be done in [name] laboratory at BloodCenter of Wisconsin according to their standard protocol. The plasma samples will be frozen and stored at -80°C at the Ohio State University until the end of the study, when samples will be delivered to [name] lab to perform the research testing.

19.2 After plasma was removed from each tube as per protocol above, the buffy coats in the tubes will be collected as much as possible and stored in RNAlater® reagent as per manufacturer's protocol. These buffy coats will be used for analysis of RNA expression in [name] laboratory at the end of the study, according to their standard protocol.

